10.7. Planned Sensitivity Analyses

The NCA analysis will be repeated based on the Safety Set (not excluding any subjects or data points, regardless of IEs or violations of entry criteria). In addition, if more than 10% of subjects have missing data on visit Day 91, 182, or 210 then the primary comparison of those outcomes between test and reference groups will be repeated based on imputed C_{91} , C_{182} , or C_{210} values, using the same imputation rules as for the end-times of partial AUCs.

10.8. [REDACTED]

11. STATISTICAL SOFTWARE

All data listings, summaries, and statistical analyses will be generated using SAS/STAT® (version 9.4 or later) or Phoenix WinNonlin® (version 8.3 or later).

12. CHANGES TO PLANNED ANALYSES

12.1. Changed from V1.0 of the SAP

The following cumulative changes were made from Version 1.0 of the SAP, prior to unblinding:

Version 2.0 (May 18, 2021)

- Section 1.2.2: Safety and local tolerability measures/parameters updated to be consistent with changes made in Protocol Amendment 02.
- Section 2.1: revised to reflect updates to assessment timepoints in Table 1 of the protocol. Specifically, addition of collection of P specimens and mood evaluation on Day 0; specimens for E2 collected on Day 0 and weeks 48, 49, 50, 51 and 52; and clarifying which visits E2 specimens will be collected if MPA or P samples are taken (starting on Day 28).
- Section 10.7: [REDACTED].

Version 3.0 (April 12, 2022)

Version 3.0 of the SAP was created to document that the above changes took place.

Version 4.0 (June 29, 2022)

Version 4.0 of the SAP clarified computation methods for apparent half-life and time above 0.2 ng/mL. The imputation of partial AE and concomitant medication start and stop dates using previous visit dates was removed as reporting date for these events was not collected. Changes to planned analyses were documented and approved prior to unblinding.

Version 5.0 (February 15, 2023)

Version 5.0 of the SAP expanded the analysis visit windows in Table 2 after blinded review of samples excluded for being out of window. These changes were not implemented for the interim analysis but were documented and approved prior to unblinding. In section 8.5, the definition of ovulation in month 12 was added as well as a definition of which subjects would be included in the denominator for the percentage calculations.

Certificate Of Completion

Envelope Id: 16B2332D2490446EBC283C9E93E0087A

Status: Completed

Subject: TV46046-10159 SAP V5.0.doc

CF02:

Project Code/Charge Code: FP0205.C01.004.004.001

Source Envelope:

Document Pages: 26

Signatures: 2

Envelope Originator:

Certificate Pages: 5

Initials: 0

[REDACTED]

AutoNav: Enabled

[REDACTED]

EnvelopeD Stamping: Enabled

[REDACTED]

Time Zone: (UTC-05:00) Eastern Time (US & Canada)

[REDACTED]

IP Address: [REDACTED]

Record Tracking

Status: Original

Holder: [REDACTED]

Location: DocuSign

2/15/2023 10:56:37 AM

Signer Events**Signature****Timestamp**

Family Health International Inc - Part 11

Security Level: Email, Account Authentication
(Required)

[REDACTED]

Sent: 2/15/2023 10:58:30 AM

[REDACTED]

Viewed: 2/17/2023 9:32:59 AM

[REDACTED]

Signed: 2/17/2023 9:34:03 AM

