9.1. Sample Size Determination and Rationale

The goal of the study is to select a dose of TV-46046 that is safe and well tolerated, and has a PK profile consistent with contraceptive protection when injected every 6 months. Recognizing that there is no formal hypothesis test on which to base same size calculations, 15 subjects per treatment group (approximately 60 in total) are expected to be sufficient to inform dose selection based on data from recent PK studies of MPA delivered subcutaneously. [REDACTED]

[REDACTED]

[REDACTED]

[REDACTED]

[REDACTED]

[REDACTED]

[REDACTED]

The intent of the study is to have a minimum of 54 subjects with evaluable data complete 32 weeks per protocol. Additional subjects may be enrolled to complete the minimum number of evaluable subjects at the discretion of the Sponsor. SRC will provide guidance regarding the value of expanding enrollment and size of such expansion to help ensure that at least 54 subjects complete 32 weeks per protocol.

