9.7. Pharmacokinetic Analysis

The following primary pharmacokinetic parameters will be calculated from concentration-time data based on the Pharmacokinetic Analysis Set:

- time to maximum observed serum drug concentration (t_{max})
- maximum observed serum drug concentration (C_{max})
- serum MPA concentration at day 91 (C_{91}), day 182 (C_{182}), and day 210 (C_{210})
- AUC_{0-182} (area under the serum drug concentration-time curve from time 0 to day 182); AUC_{0-210} (AUC from time 0 to day 210); and $AUC_{0-\infty}$ (AUC extrapolated to infinity)
- apparent terminal half-life ($t_{1/2}$)

Among these primary pharmacokinetics parameters, non-compartmental methods will be used to estimate AUC values and $t_{1/2}$. The other estimates (t_{max} , C_{max} , C_{91} , C_{182} , and C_{210}) will be based on observed values where possible. No formal hypothesis tests of pharmacokinetic data are planned. Parameter estimates will be summarized by treatment group for each dose level using descriptive statistics, including n, mean, SD, standard error, geometric mean, geometric coefficient of variation, harmonic mean (for $t_{1/2}$), median, minimum, maximum, and 95% confidence intervals (CIs) for means. Graphical displays will include individual and geometric mean pharmacokinetics profiles.

PK comparisons between each dose of test formulation (TV46046) and the reference product (Depo-subQ Provera 104) will be made based on geometric mean ratios (test/reference) and 90% CIs with the following MPA exposure parameters: C_{max} , C_{91} , C_{182} , C_{210} , AUC_{0-182} , AUC_{0-210} , and $AUC_{0-\infty}$.

Other pharmacokinetic parameters (eg, steady-state trough concentrations) may be calculated using non-compartmental methods or non-linear mixed effects models to inform dose selection.

Effects of subject characteristics (eg, BMI) on pharmacokinetics of MPA will likewise be explored using non-linear mixed effects models as the data permits.

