Statistical Analysis Plan Version 5.0

Pharmacokinetics Study–Healthy Subjects

Study TV46046-WH-10159

INTRODUCTION

This Statistical Analysis Plan (SAP) describes the planned analysis for *A Randomized, Dose-range Finding Study to Evaluate Pharmacokinetics of Medroxyprogesterone Acetate Following a Single Subcutaneous Administration of TV-46046 in Healthy Women of Reproductive Age*. The study is sponsored by Teva Branded Pharmaceutical Products R&D, Inc. and is implemented by FHI 360.

The reader of this SAP is encouraged to read the protocol for details on the conduct of this study, the operational aspects of clinical assessments, and the timing for completing the participation of a subject in this study. Version 1.0 of the SAP expands upon the analysis of primary and secondary endpoints outlined in Protocol Amendment 01 (the current version at the time of first subject enrolled), including definitions of estimands and methods for handling missing data and intercurrent events. When differences exist in descriptions or explanations provided in the study protocol and this Statistical Analysis Plan, the SAP prevails; any such differences will be explained in the Clinical Study Report (CSR).

Future changes to the SAP (e.g., to address amendments to the protocol) and their temporal relationship to unblinding will be documented in Section 12 and detailed in the CSR. Mock tables, figures and listings will be approved by the Coordinating Investigator prior to un-blinding of study statisticians and maintained in a separate document.

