2.3. Blinded Data Review

Prior to the first planned interim analysis, study data will be reviewed by the Coordinating Investigator and Lead Biostatistician or their designee(s) to inform analysis decisions. The Lead Biostatistician will be responsible for developing blinded listings for this review and will document the Coordinating Investigator's decisions prior to unblinding. These reviews will include (but not necessarily be limited to) important protocol deviations for inclusion/exclusion of subjects and/or data points from the primary analysis sets, assessment of potential outliers, and any necessary adjustments to imputation rules for missing MPA results due to out of window visits. Blinded data reviews may likewise occur to inform clinical queries to the site.

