4.4. Study Days and Visits

For purposes of analysis, the number of days post-injection on which an event occurs or an outcome is assessed will be calculated as the date of the event or outcome, minus the date of treatment initiation; a negative day indicates an event prior to study drug administration. When appropriate, fractions of study days will be computed based on the time (in hours and minutes) of a subject's injection and the time of her event or outcome assessment.

Although actual MPA sampling times will be used in applicable pharmacokinetics analyses (e.g., when computing AUC values), sampling times will be assigned to visit windows when reporting by-visit summaries of MPA concentrations (e.g., C_{182}). In order to maximize available data, the window periods used in these by-visit summaries may be wider than the target visit windows specified in the protocol (see [Table 2](#)).

Table 2. Pharmacokinetic data visit windows

Days since Treatment Initiation	Protocol Target	Visit Window	Visit-specific Analyses
1, 2	± 1 hour	+/ - 3 hours	
3, 5, 7	± 3 hours	+/ - 6 hours	
10, 12, 14, 18	± 24 hours	+/ - 24 hours	
21 and after (except days 91 and 182)	± 48 hours	+/ - 168 hours	
91, 182	± 48 hours	-84 / +168 hours	

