10.5. Noncompartmental Analysis

The following protocol-specified pharmacokinetic parameters will be estimated based on NCA: C_{max} , T_{max} , C_{91} , C_{182} , C_{210} , AUC_{0-182} , AUC_{0-210} , $AUC_{0-\infty}$, and the apparent terminal half-life (computed as $\log_e[2]/\lambda$). Additional estimates will include AUC through day of last quantifiable sample (AUC_{0-last}), and time above 0.2 ng/mL (extrapolated to infinity). Detailed rules used to estimate these parameters, and conditions that must be met to report the estimate, are as follows:

- C_{max} will be based on the maximum observed MPA concentration for subjects who a) provide at least one MPA result after their highest observed concentration and b) do not use a concomitant medication known to impact the pharmacokinetics of MPA before the occurrence of C_{max} . Values of C_{max} for subjects who fail to meet these two criteria will be considered non-evaluable and excluded from the primary pharmacokinetic analysis.
- T_{max} will be based on the day (rounded to the first decimal place) when C_{max} was initially observed. Values of T_{max} for subjects who's C_{max} is non-evaluable (per above) will be excluded from primary analyses.
- C_{91} , C_{182} , and C_{210} will be based on evaluable results in the corresponding pre-defined visit windows ([Table 2](#)). If a subject has more than one MPA result in the same visit window, then the value closest to the nominal time will be used.
- λ will be estimated as minus the slope of the terminal phase, based on the last three or more log-transformed MPA concentrations after C_{max} but on or before T_{last} , regressed on time. The specific number of time points used to compute λ will be determined based on the unweighted regression with largest adjusted R^2 . If the estimated slope is not negative, or if fewer than three time points are available for estimating λ , then no value will be reported.
- Partial AUC values will be computed using the ‘linear up log down’ rule as implemented in Phoenix WinNonLin (version 8.3 or higher). No AUC value will be reported if C_{max} was not estimable per above.
- $AUC_{0-\infty}$ will be computed as $AUC_{0-last} + C_{last}/\lambda$, where C_{last} is the last quantifiable drug concentration measurement

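### Do the wider Version 5.0 visit windows for C91, C182 and C210 make these primary concentrations unreliable?

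*SAP*

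**What the plan says.** SAP Section 1.1.2 lists C91, C182 and C210 among the primary endpoints. SAP Section 10.5 says that they "will be based on evaluable results in the corresponding pre-defined visit windows", and that the result nearest the nominal time is used if a window holds more than one. Protocol Section 9.7 likewise says that these estimates "will be based on observed values where possible".

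SAP Table 2 (Section 4.4) sets the windows at -84/+168 hours for Days 91 and 182 and ±168 hours for Day 210, against a protocol target of ±48 hours. Section 4.4 gives the reason, to make the most of the available data, and says openly that "the window periods used in these by-visit summaries may be wider than the target visit windows specified in the protocol". AUC values use actual sampling times.

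SAP Section 10.7 adds a sensitivity analysis: "if more than 10% of subjects have missing data on visit Day 91, 182, or 210 then the primary comparison of those outcomes" is repeated with imputed values.

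SAP Section 12.1, under Version 5.0 (February 15, 2023), says that this version "expanded the analysis visit windows in Table 2 after blinded review of samples excluded for being out of window". It adds that the change was not applied at the interim analysis and was approved before unblinding. The SAP Introduction says of SAP changes that "their temporal relationship to unblinding will be documented in Section 12 and detailed in the CSR". SAP Section 2.2 ends the analysis team's blinding at the first interim analysis.

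**The concern.** On a declining curve, a late sample reads low. For Days 91 and 182 the window reaches twice as far late as early, so the largest possible errors all point downward. These concentrations, and the ratio of test C182 to reference C91, bear most directly on the 6-month question.

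The safeguard also appears to miss the affected samples. The blinded review in SAP Section 2.3 covers "any necessary adjustments to imputation rules for missing MPA results due to out of window visits", so an out-of-window sample used to count as missing. Inside a wider window it counts as observed, drops out of the 10% count in Section 10.7 and is never imputed. Section 10.7 does not say whether 10% is judged overall or by arm.

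Finally, if the windows were approved before the interim, Section 12 does not explain why the interim did not use them. If they were approved afterwards, the statement that approval came before unblinding needs squaring with Section 2.2. Without dates for the approval, the interim and unblinding, a reader cannot check which applies.

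**Working it through.** **1. Where the window limits come from.** 168 h / 24 = 7 days, 84 h / 24 = 3.5 days, and 48 h / 24 = 2 days. The neighbouring scheduled samples are in SAP Section 2.1.

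| Endpoint | Neighbouring samples (days) | Midpoints (days) | Offset from nominal |
|---|---|---|---|
| C91 | 84, 105 | 87.5, 98 | -3.5 / +7 |
| C182 | 175, 196 | 178.5, 189 | -3.5 / +7 |
| C210 | 196, 224 | 203, 217 | -7 / +7 |

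The offsets match Table 2 exactly. The asymmetry for Days 91 and 182 comes from the sampling schedule.

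**2. Error in one sample.** Assume log-linear decline with half-life h. A sample drawn d days late is then off by 2^(-d/h) - 1. Protocol Section 1.2.2.1 gives h = 82.87 days (undiluted) and 42.34 days (saline-diluted) from a 12-subject study at 120 mg.

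| Timing | h = 82.87 | h = 42.34 |
|---|---|---|
| 7 days late | -5.7% | -10.8% |
| 2 days late (protocol target) | -1.7% | -3.2% |
| 3.5 days early | +3.0% | +5.9% |
| 7 days early (C210 only) | +6.0% | +12.1% |

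The test product is 300 mg/mL (120/0.4 = 180/0.6 = 240/0.8 = 300) and no dilution is described, so the first column is the closer guide. The documents give no half-life for the reference product.

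**3. Effect on a group geometric mean.** If a fraction f of an arm is a full 7 days late and the rest are on time, the shift is 2^(-7f/h) - 1. The fractions are assumptions.

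| f | h = 82.87 | h = 42.34 |
|---|---|---|
| 10% | -0.6% | -1.1% |
| 30% | -1.7% | -3.4% |
| 50% | -2.9% | -5.6% |

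In a test/reference ratio, only the difference between the two arms' shifts remains. All arms follow one visit schedule.

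**4. Comparison with sampling error.** For a ratio of geometric means with 15 per arm, the 90% CI factor is exp[t(0.95, 28) × sqrt(ln(1 + CV²)) × sqrt(2/15)]. The CV is an assumption.

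- CV 30%: 1.20, so limits at 0.83 and 1.20 times the estimate.
- CV 60%: 1.41, so limits at 0.71 and 1.41 times the estimate.

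A shift of 0.6% to 3.4% is small against either interval.

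**5. The 0.2 ng/mL cut-off.** 0.2 × 2^(7/82.87) = 0.212 and 0.2 × 2^(7/42.34) = 0.224. A woman whose nominal-day value lies between 0.200 and 0.212 (or 0.224) would read below 0.2 if sampled 7 days late. The band is narrow. SAP Section 10.5 also estimates time at or above 0.2 ng/mL by interpolation between samples, in every case and without visit windows.

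**6. The 10% trigger.** With 60 subjects, 6/60 = 10.0% does not exceed the threshold and 7/60 = 11.7% does. Judged by arm, 2/15 = 13.3% does. Six missing women all in one arm would be 6/15 = 40% of that arm without triggering an overall rule.

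**The case for a change.** The strongest case for acting is that the remedy is cheap. Bracketing samples are scheduled for every subject, so concentrations interpolated to the nominal day could be tabulated beside the observed ones, along with results under the interim windows. A few dates would settle the blinding question. The interim and final tables will also differ in their window rule, and the visible text plans no display that separates this from new data.

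The facts behind this stand. No time adjustment is stated for the three concentrations, the widening makes the trigger in Section 10.7 less likely to fire, and the dates are absent. Three things limit their weight.

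- **Dose selection.** The planned interim, which serves the choice of a dose for the pivotal study, did not use the wider windows. It falls after at least 80% of treated subjects could have reached 7.5 months (about 228 days), beyond the last edge of the Day 210 window (Day 217). Results under the earlier windows therefore already exist for most subjects.
- **The trigger example.** Six missing values of 60 comes from Protocol Section 9.1: "The intent of the study is to have a minimum of 54 subjects with evaluable data complete 32 weeks per protocol". That is a completion target, not a forecast of missed visits, and the same section allows extra enrolment. All six in one arm is an extreme case.
- **What is visible.** SAP Section 10.8 is redacted, the imputation rule for the end-times of partial AUCs is not shown in the public copy, and the mock tables are kept in a separate document. It cannot be established that no other time-corrected display is planned.

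On blinding, Section 12.1 does state that approval came before unblinding, and the Introduction leaves the detail to the study report. Nothing shows a change made after unblinding. Limits that equal the schedule midpoints and apply alike to every arm also leave little room for tuning to the results.

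**Conclusion.** No change to the plan is needed. Taking the observed value nearest the nominal time within midpoint windows is ordinary practice and agrees with the protocol's preference for observed concentrations. The wider windows are a fair trade: a small, bounded timing error in some values in return for keeping subjects who would otherwise be lost from arms of about 15.

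The error is about 6% for a sample 7 days late. It is 0.6% to 1.7% on an arm's geometric mean with the undiluted half-life, and at most 3.4% with the faster one. This assumes log-linear decline, half-lives from one small study at one dose, and 10% to 30% of an arm at the extreme late limit. The earlier windows are not in the documents, so the widening itself cannot be measured. The study has no hypothesis test, and its ratio intervals are far wider than these shifts.

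The denominator of the 10% rule and the dates of approval, interim and unblinding are missing details. An analyst would settle the first without difficulty, and the study report is already committed to the timing of changes relative to unblinding. An interpolated or ±48-hour display would be a harmless extra, but the primary analysis is sound without it.
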